Survey Objective (SO) 1. To measure validated treatment coverage of PZQ and ALB in SAC, and adults relative to coverage targets

SO 2. To compare reported and validated coverage of PZQ and ALB for SAC and adults

SO 3. To assess coverage in SAC and adults disaggregated by gender

SO 4. To assess coverage in SAC disaggregated by school attendance

SO 5. Collect information on why targeted eligible individuals did not receive or accept treatment

- SO 6. To assess the impact of radio campaigns on improving knowledge about schistosomiasis
- SO 7. To assess whether radio campaigns improved attendance/coverage of treatment with PZQ and ALB

Where validated coverage rate is defined as:

Total number of interviewed individuals that ingested the target drug Total number of interviewed individuals * 100 %

Note that people interviewed but with missing information on whether they ingested the drug will be assumed to have **not** taken the drug for the purposes of calculating validated coverage.

Study Design

Overview

The coverage survey will take place in nine implementation units (IUs) known as the district. Each IU will be considered separately. Within each IU, the survey will be household (HH) based in randomly selected villages. See Appendix D for a detailed explanation of the statistical approach to the coverage survey.

Survey team

Interviewers must not have been involved in any previous activities related to the NTD programme, specifically the MDA, to ensure that they remain unbiased.

Selection of enumerators will be done by the Programme Managers, ensuring that none of the interviewers were involved with the MDA in July 2017. The majority of interviewers have experience in coverage surveys, but everyone will attend compulsory training to ensure standardisation of knowledge and ability to carry out coverage surveys. Training will include teaching about schistosomiasis and soil transmitted helminth infections as well as familiarisation with the health questionnaires and the phones that the information will be stored on.

Although programme managers will not take part in any of the individual interviews in interviewee households, they will facilitate in the training and logistics of the survey as well as support the teams of enumerators if problems arise.

See Appendix A for more details of the survey teams and logistics.

Timing of survey

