APPENDIX A: Field team planning manual

Survey team composition

Include a brief description of the survey teams: The participants were identified by the Malawi program manager as people with skills and experience relevant for the activity. The backgrounds from the participants ranged from IT Graduates, retired teachers to experienced Nurses from within the MoH.

Survey teams will be made up of students and people known to the program with interview skills but had no part in the MDA.

There will be 6 teams made up of 1 team leader, 3 interviewers and a driver.

The survey will take 5 weeks to complete all districts working Monday – Saturday each week.

Survey team training

Training for the survey will be conducted by the SCI PM, MoH PM with additional input from other Program staff. Below are links to the various training materials that will be used. Each interviewer will be provided with an Interviewer manual and cheat sheet for using the phones.

The questionnaire will be translated prior to the training and will be reviewed during the training to ensure they are fully understood. Each team will be provided with the same dose pole that was used during each distribution (MDA), samples of each of the drugs that were provided, and examples of the posters and leaflets used during social mobilization. These will act as visual cues to the individuals in each HH.

Training Material

Agenda:

https://imperiallondon.sharepoint.com/sites/fom/SCI/The%20Hub/MWI_Coverage%20Survey%20Training% 20Agenda_OCT%202017.docx

Schisto Overview:

https://imperiallondon.sharepoint.com/sites/fom/SCI/The%20Hub/GLO_Schisto%20Program%20Overview% 20for%20Coverage%20Survey%20Training.pptx

Coverage Survey Overview:

https://imperiallondon.sharepoint.com/sites/fom/SCI/The%20Hub/GLO_PP_Coverage%20Survey%20Trainin g%20Template.pptx

Household Selection Exercise: https://imperiallondon.sharepoint.com/sites/fom/SCI/The%20Hub/MDG-%20HH%20selection%20exercise.pptx

Phone Use:

https://imperiallondon.sharepoint.com/sites/fom/SCI/The%20Hub/TOOL_Coverage_SurveyCTO_Cheat_She et_EN.docx

Practice Scenarios:

https://imperiallondon.sharepoint.com/sites/fom/SCI/The%20Hub/GLO_Coverage%20Survey%20Training%2 OPractice%20Household%20Scenarios_EN.docx

Coverage Manual:

https://imperiallondon.sharepoint.com/sites/fom/SCI/The%20Hub/MWI%20Interviewer%20Manual%20201 7.docx?d=w9fd6a56081c14123b115a778483f6a84&csf=1

Timetable of activities

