- If an individual is away from the house (e.g. at school), go to try to find them if permission from the head of the HH has been obtained.
- If they still cannot be interviewed then DO NOT replace them with another individual. Record them on the survey form as not being interviewed and the reason why.

Interviewing selected individuals

- Interview the randomly selected individuals using the phones or paper forms
- Interviews should be conducted with each person privately; parents can accompany children.
- Avoid leading questions or providing the HH with information which later you will be asking them to provide to you either as an answer, or to check their responses. Use visual cues as much as possible (dose poles, drugs etc)
- **DO NOT** read the multiple-choice options to the interviewee or suggest an answer
- Wait for the interviewee to provide an answer and then choose the most appropriate option on the phone or from the codes provided with the paper forms
- If using paper forms, be very careful when answering questions with multiple parts that no contradictory answers are given e.g. person says that they did take drugs but also give a reason why they didn't take drugs

Note: The survey can be conducted by either one (1) or both interviewers at a time. If the interviewers feel confident that they can conduct the interview alone then the other interviewer and field supervisor can proceed to the next HH according to the sampling protocol.

Finishing the survey

- After everyone selected has been interviewed and all the responses recorded on the data collection form thank everyone for their assistance and leave the HH.
- Move on to the next selected HH and repeat.

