(Tick one box)	Other
If person not interviewed and reason no	
Interview 'other': Other reason no interviewed?	
(Enter reason)	
Interview start time (HH.MM)	
Is this person being interviewed	☐ Yes
confidentially?	
Consent received?	
	L No
Participant age? (Enter one number)	
Sex (M/F)? (Tick one box)	
	L Female
What is your occupation?	
(ENTER CODE)	
Adults only, if occupation is other:	
(write answer)	
Adult female only:	
Were you pregnant or breastfeeding in July	
2017? Children only:	
Have you attended school in the last school	
year: January 2017 to December 2017?	LJ No
(Tick one box)	
If attended school in last school year: What type of school do you attend?	
(ENTER CODE)	
How did you hear about the mass	
treatment? (ENTER CODE)	

English Questions	Participant
If heard about mass treatment is other:	
How did you hear about the mass treatment	
- other : (write answer)	
Individual knowledge of the schistosomiasis	
mass treatment	
show particpants props and (tick all objects	
recognised, or 'none' if don't recognise any)	Dose pole
	□ None of above
Did you swallow PZQ at the mass treatment?	The Yes
(show dose pole/tablets)	
(Tick one box)	
If did not swallow PZQ:	
Reasons for not swallowing PZQ	
If did not swallow PZQ, and other reason for	
not swallowing PZQ:	
Other reasons for not swallowing PZQ	
(write answer)	
IJ Swallowed P2Q: Where did you take the P7O?	
(ENTER CODE)	
Did you swallow ALB at the mass treatment	Tes Yes
(show tablet)?	
(Tick one box)	
If did not swallow ALB:	
Reasons for not swallowing ALB	
If did not swallow ALB. and other reason for	
not swallowing ALB:	
Other reasons for not swallowing ALB	
(write answer)	
If swallowed ALB: Where did you take the ALB?	
(ENTER CODE)	
If swallowed PZQ or ALB:	
How did you take the PZQ and ALB tablets?	
If swallowed PZQ or ALB:	
swallowed the tablets?	
(Tick one box)	LJ No

English Questions	Participant
If swallowed PZQ or ALB/MEB: Had you eaten in the two hours before you took the tablets? (Tick one box)	☐ Yes ☐ No
Who decided whether you took the treatment or not? (ENTER CODE)	
If who decided is other: Who decided whether you took the treatment or not - other? (write answer)	
Did you know beforehand when and where the MDA would take place? (ENTER CODE)	
How far was the distribution point from your	
What is the language you use to communicate at home?	 Chewa / Nyanja Yao Lomwe Nkhonde Ngoni Tumbuka Sena Nyakusa Tonga Lambya Senga Sukwa Other

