How frequently do you listen to the radio during a week? READ OPTIONS	 More than once a day At least once a day 2 or 3 times per week Once a week Never
[IF AT LEAST ONCE A WEEK] What radio station do you most commonly listen to? WRITE ANSWER	 Zodiak Station MBC Radio Dzimwe Community Radio Nkhota–Kota Radio Neno Community Radio Mzati Community Radio Dziko Community Radio

English Questions	Participant
	🗖 Mzimba Radio
	Dinosaur Community Radio
	Other
What other radio stations do you listen to?	Zodiak Station
MENTIONED AND STATE OTHERS	MBC Radio
	Dzimwe Community Radio
	Nkhota–Kota Radio
	Neno Community Radio
	Mzati Community Radio
	Dziko Community Radio
	🗖 Mzimba Radio
	Dinosaur Community Radio
	Other
The proceeding questions are played with	
radioclips (10seconds in length) in the	
During June and July 2017, the Ministry of	
Health broadcasted a series of radio shows	
schistosomiasis I will now ask you a few	
questions about these broadcastings.	
During that time, do you recall having listed to	T Yes
this radio clip: [PLAY CLIP 1: Mother	
testimonial]?	
[IF YES] Can you tell us what you recall was	A Mother describes a conversation with a doctor
TICK ALL ELEMENTS RESPONDENT IDENTIFIES	Malawi's children have SCH
AS PART OF CLIP	SCH affect mental and physical health
	SCH may show no symptoms
	Children need treatment (medicine) every year
	Distribution is for free
	Children who don't attend school can receive treatment
	Children need to eat prior to MDA.
During that time, do you recall having listed to	The second secon
this radio clip: [PLAY CLIP 2: Doctor testimonial]?	□ No
[IF YES] Can you tell us what you recall was mentioned in this radio clip?	A doctor talks to the audience about SCH
TICK ALL ELEMENTS RESPONDENT IDENTIFIES	Malawi's children have SCH
AS PART OF CLIP	SCH affect mental and physical health
	SCH may show no symptoms

English Questions	Participant
	Children need treatment (medicine) every year
	Distribution is for free
	Children who don't attend school can receive treatment
	Children need to eat prior to MDA.
During that time, do you recall having listed to	T Yes
this radio clip: [PLAY CLIP 3: Give me my broakfast]?	□ No
IF RECALLED FITHER CLIP 1, 2 OR 31 Did you	
discuss the content of any of those clips with	Yes
your family, friends or neighbours?	L No
[IF YES] What topics did you discuss with them?	MDA dates
TICK ALL TOPICS MENTIONED	Malawi's children have SCH
	SCH affect mental and physical health
	SCH may show no symptoms

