	Children need treatment (medicine) every year
	Distribution is for free
	Children who don't attend school can receive treatment
	Children need to eat prior to MDA.
	Other (specify)
Apart from the clips we played to you, did you	T Yes
lune and July 2017 about MDAs against [LOCA]	□ No
TERM FOR SCH]?	
[IF YES] What information was provided in these	MDA dates
radio programmes?	Malawi's children have SCH
	SCH affect mental and physical health
	SCH may show no symptoms
	Children need treatment (medicine) every year
	Distribution is for free
	Children who don't attend school can receive treatment
	Children need to eat prior to MDA.
	Uther (specify)

Individual Answer Code

Answer codes for Household an	d Individual questions
23a: What is your occupation?	24b: What type of school do you attend?
1. Farmer	1. Primary (public or private)
2. Merchant	2. Secondary (public or private)
3. Health worker	3. Religious school
4. Housewife	
5. Student	
6. Fisherman	
7. Medicines distributor	
8. Teacher	
9. Village Head	
10. Does not work	
11. Other (please specify)	
25a. How did you hear about the drug	27b: Reasons for not swallowing PZQ
distribution?	28b: Reasons for not swallowing ALB/MEB
1. Teacher	1. Too young
2. Village Meeting	2. Too old
3. Posters / flyers	3. Pregnant
4. Health professional	4. Breast feeding
5. Newspaper	5. Too sick
6. Radio	6. Feels healthy
7. TV	7. Fear of side effects
8. Town crier (loud speaker)	8. Bad smell or taste
9. Place of worship	9. Tablets are too large
10. Banner	10. Rumours
11. Other (please specify)	11. Does not know
	12. Drugs ran out
	13. Was at work
	14. Not living in the village at time of MDA
	15. Absent from school on day of MDA
	16. Does not attend school
	17. There was no MDA
	18. Had not heard about MDA
	19. Too far from distribution point
	20. Refused to answer
	21. Was not invited to MDA
	22. Had not eaten before MDA
	23. Too many tablets
	24. Medicine does not work
	25. Other (please specify)

27d: Where did you take PZQ?	29: How did you take the PZQ and ALB tablets?
28d: Where did you take ALB?	1. All at the same time
1. School	2. I took them all throughout the day but not all at
2. Home (door-to-door)	the same time
3. House of the village head	3. I took them all but not on the same day
4. Central point in the village	4. One tablet a day until they were all finished
5. Local Health Centre	5. I took some but not all of them
6. District Clinic	6. I was given the tablets but did not swallow them
7. Other	7. Do not remember

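### Campaign posters and leaflets may be shown before the unaided message-content items, which can prime the SO6 message data

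*Protocol*

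**What the plan says.** **Cue kit.** Protocol Appendix A, Survey team training, supplies each team with the dose pole, samples of the drugs and "examples of the posters and leaflets used during social mobilization. These will act as visual cues to the individuals in each HH".

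**Interviewer rules.** Appendix B, under the instructions for interviewing selected individuals, says: "Avoid leading questions or providing the HH with information which later you will be asking them to provide". The same bullet encourages heavy use of visual cues. It names dose poles and drugs as examples and leaves the list open. A separate bullet forbids reading out the answer options.

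**Form order.** In the Appendix C individual questionnaire, the question on the source of information ("How did you hear about the mass" treatment) comes first. Next is the props item, "show particpants props and (tick all objects" recognised). The PZQ and ALB swallowing items follow, with the dose pole and tablets named as the things to show. The radio section comes later, introduced by "The proceeding questions are played with" radio clips of 10 seconds. It covers recognition of three clips, content of clips 1 and 2, topics discussed with others, and content of other broadcasts. A typical tick-box is "Children need treatment (medicine) every year".

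**Objectives.** SO6 is "To assess the impact of radio campaigns on improving knowledge about schistosomiasis". SO7 is "To assess whether radio campaigns improved attendance/coverage of treatment with PZQ and ALB".

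**The concern.** The content items are meant to be unaided: the respondent names messages and the interviewer ticks them. If a leaflet carrying the same messages has been in front of the respondent a few minutes earlier, a tick may reflect the leaflet and not the radio campaign. Apart from recognition of props, these tick-lists are the only legible items on the form that record what a respondent knows of the campaign's messages, so they are the main data for SO6. The survey falls about 4 months after the MDA by the protocol's own count, so unaided memory may be weak and a fresh cue influential. The legible form does not record which printed text a respondent read, so the analysis could not separate the two sources afterwards.

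**Working it through.** The protocol gives no figure on this point, so the check traces the order of the instructions and items.

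1. **Is the print meant to be seen by respondents?** Yes. Appendix A makes it a cue for individuals in each household.

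2. **When is it seen?** The props item is the only place on the form where props are shown generally. It precedes the swallowing items and the whole radio section. Its tick-list is broken in the text available here: only the dose pole and a none-of-these option can be read. Whether posters and leaflets are on that list is therefore unknown, but Appendix A provides for their use either way.

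3. **Is it withdrawn before the content items?** No section says so.

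4. **Which later items could it prime?**

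| Item | Position relative to props | Open to priming by print? |
|---|---|---|
| How the person heard of the treatment | Before | No, if form order is kept and the person has not already seen the kit |
| Swallowed PZQ, ALB | After | Print does not supply the answer; dose pole and tablets are the named cues |
| Knew beforehand when and where | After | Little: a self-rating, with no date or place asked for or scored |
| Recognition of clips 1 to 3 | After | Print does not supply the answer; the audio is played |
| Content of clips 1 and 2 | After | Partly: the excerpt has just been played, so print matters only for content beyond it |
| Topics discussed | After | Yes, in part: asked about the person's own conversations, with no further clip played |
| Content of other broadcasts | After | Yes: no clip is played for it |

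5. **Why the clip excerpt does not settle it.** The section on the 2017 MDA describes 1-minute clips, and the interview plays 10 seconds: 10/60, or one sixth. The tick-lists for clips 1 and 2 cover seven messages besides the description of the speaker. An excerpt of that length is unlikely to carry them all. Content beyond the excerpt is what would support a claim to have heard the broadcast, and print could supply it.

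6. **Spread within a household.** Two adults and all school-aged children are interviewed, and a parent may sit in with a child. A parent who sees the kit then could be primed before their own interview, including at the source-of-information item.

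7. **Direction and size.** Let p be the share of those asked who would name a message unaided, and c the share of the remainder who take it from the print. The recorded share is p + c(1 − p), so any bias is upward, by c(1 − p). The protocol gives neither p nor c. If the print does not carry the message, c = 0 and there is no bias.

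**The case against.** Several points can fairly be made against this.

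- **The leaflet text is not in the protocol.** Overlap with the radio messages is plausible but assumed. This stands, and it limits the point to a risk.
- **Appendix B already restrains interviewers.** The examples it gives of cues are dose poles and drugs, and the bullet opens by barring information that will be asked for later. This stands in part. Appendix A nonetheless names posters and leaflets as cues, and no instruction says when to show them. An interviewer following Appendix A can break the Appendix B rule without knowing it.
- **For clips 1 and 2 the excerpt is the more direct source of answers.** This stands for content within the excerpt, and moving the leaflet does not cure it. It does not cover content beyond the excerpt or the two items for which no clip is played.

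Two stronger readings are tempting. A reader might infer that a knowledge gap between radio-exposed and unexposed people would be shrunk. The form does not produce that contrast: every content item is asked only of people who report having heard a clip or another broadcast, so the unexposed are never asked. A reader might also infer that the SO6 and SO7 data are certain to be contaminated. The protocol does not support that for SO6, because the printed content is unseen. For SO7 it supports still less: exposure can be taken from recognition of a played clip and the outcome from the swallowing items, and a leaflet answers neither.

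**Conclusion.** The protocol's cue instruction and its interviewing rule conflict, and the form order lets the conflict reach the items that supply the SO6 message data. The items at risk are content of other broadcasts, topics discussed, and clip content beyond the 10-second excerpt. The effect, if present, inflates apparent message recall among people who report exposure. It may also vary with literacy and with how freely an interviewer shows the kit. Its size cannot be quantified from the protocol. SO7 is affected only in that content recall becomes a weaker check on claimed exposure. The point does not call the coverage estimates into question. It rests on one assumption, that the posters or leaflets carry at least some of the listed messages. It is worth correcting before fieldwork because the remedy is nearly free and the priming cannot be undone afterwards.

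**What to change.** In Appendix A (Survey team training) and Appendix B (interviewing selected individuals), state that the cues used before and during the ingestion items are limited to the dose pole and tablets, which the form already names there. State that any poster or leaflet, and any recognition item about one, comes only after the radio section is finished. Where several people in a household are interviewed, keep the print out of sight of anyone still to be interviewed. If the props item in Appendix C includes posters or leaflets, move that part to the end of the individual form.

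The cost is a sentence in each appendix and, at most, one moved item. The downside is slightly less cueing about which campaign is meant when people are asked whether they swallowed the drugs; the dose pole and tablets remain for that purpose. The change does not address answers taken from the clip excerpt itself.

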APPENDIX B: Malawi 2017 Coverage survey interviewer manual

Before arriving at the village

- The team leader should ensure that the village leader is notified of the study at least one week before the survey. The district coordinator may be able to help with this.
- The village leader should be asked if they can provide a list of all households in the village when the team arrives

Arriving at the village

- It is important to be at the village when people are available. This means interviewers should be in the village and ready to start at 8am every day.
- The first thing the team should do when arriving at the village is to seek out the head of the village:
 - 1. Introduce the team and ask for permission to survey
 - 2. Ask the head of the village for a list of houses in the village
 - 3. If a list of houses is available, select households using the 'village list' method
 - 4. If a list of households is not available, select households using the 'modified random walk' method
- The team leader will be responsible for completing the village questionnaire by interviewing the village leader:
 - The **GPS co-ordinates** of the village should be entered on **arrival and departure** if the data is being collected on paper forms

What to do if a village cannot be visited

If a selected village cannot be visited for security or other unpredictable reasons, replaced the village with the first reserve village in the same district that hasn't yet been visited.

Selected villages should only be replaced with those on the reserve list in extreme circumstances where it is impossible to survey that village, and not for reasons of distance, access difficulty and so on. It is important to document in the field report any villages that have been replaced and the reason for this replacement, as this could be a reason for biased coverage results.

Selecting households to interview

20 households will be randomly selected per village.

Definition of a household

We define a HH to be "a group of persons who normally live and eat their meals together in the household, and did so during the time of the survey". These people may or may not be related by blood, but make common provision for food or essentials for living and they have only one person whom they all regard as head of the household"

If the HH comprises of one man with more than one wife then all wives and any children should classified as one HH.

In some villages, several HHs, normally within the extended family, share the same compound. At the selected compound, if there are a number of HHs which could be selected, one HH should be randomly selected from the HHs in the compound (selection should not take the most senior, but be done by numbering the HHs and randomly selecting pieces of papers with the respective numbers written on them).

Selecting households method 1: Village lists

The village list selection of HHs is the preferred selection method. At village level, the village chief or equivalent administrative leader will be approached for a list of all HHs in the village. Team leaders must ensure that this HH list is fully up to date and captures all HHs within the area.

Sampling using the village list is when every *h* HHs in the village are sampled with the initial HH being a random number between 1 and *h*, where *h* is the sampling fraction as detailed below.

The steps to take for sampling using the village list are:

- 1. Find the total number of HHs in the village from the village list
- 2. Calculate the sampling fraction (*h*) using the equation below. Non-whole numbers should be rounded down.

$h = \frac{Total number of households in village}{Number of households to survey}$

- 3. Select the first HH by randomly selecting a number between 1 and *h*. Random number selection can be done in the field by writing numbers on pieces of paper, folding them up, placing them in a container and mixing before drawing one out at random, and then selecting the HH that is on this row in the village list.
- 4. The second HH to sample should be the initial number + *h*.
- 5. Sampling should then proceed in this manner with every h^{th} HH being sampled.

Example of selection of HHs with a village list:

- 1. The protocol is to sample 12 HHs in the village.
- 2. The village list shows that there are 200 HHs in the village.
- 3. Therefore h = 200 / 12 = 16.66, which is rounded down to 16
- 4. The numbers 1 16 are written on pieces of paper, folded up and placed in a container and mixed up. The random piece of paper drawn out is 5.
- 5. The HH on the 5th row of the village list is identified.
- The second HH to select for interviews is 5 + 16 = 21. The HH on the 21st row of the village list is identified.
- Sampling then continues to HHs 37 (= 21 + 16), 53, 69, 85, 101, 117, 133, 149, 165, 181 and 197 giving 12 HHs sampled in total.

Random selection to	Select house	every 16 th (21 = 5 + 16)		
	K			
House	1 House 21	House 41	House 61	House 81
House	2 House 22	House 42	House 62	House 82
House	3 House 23	House 43	House 63	House 83
Viouse	4 House 24	House 44	House 64	House 84
House	5 House 25	House 45	House 65	House 85
House	6 House 26	House 46	House 66	House 86
House	7 House 27	House 47	House 67	House 87
House	8 House 28	House 48	House 68	House 88
House	9 House 29	House 49	House 69	House 89
House	LO House 30	House 50	House 70	House 90
House	L1 House 31	House 51	House 71	House 91
House	L2 House 32	House 52	House 72	House 92
House	L3 House 33	House 53	House 73	House 93
House	L4 House 34	House 54	House 74	House 94
House	L5 House 35	House 55	House 75	House 95
House	L6 House 36	House 56	House 76	House 96
House	L7 House 37	House 57	House 77	House 97
House	L8 House 38	House 58	House 78	House 98
House	L9 House 39	House 59	House 79	House 99
House	20 House 40	House 60	House 80	House 100

Selecting households method 2: Modified random walk

If there are no village lists available then the HHs can be selected using the Modified Random Walk Procedure. The first HH is determined using the traditional spin the bottle method.

The steps for carrying out a random walk are:

- 1. Identify a central point (i.e. central meeting place, house of the village chief) within the village.
- 2. Spin a bottle/pen at this central point to randomly select a direction. If there is no road in the direction indicated by the bottle, move the bottle clockwise until a road is encountered.
- 3. Count all HHs along the direction indicated by the bottle between the central point and the village boundary. **Do NOT count empty/destroyed houses, businesses, or administrative buildings**. It is important to remember which HHs were included in the counting. A map indicating the HHs and their numbers should be drawn up.
- 4. The sampling fraction *h* should then be calculated using the equation below. Non whole numbers should be rounded down.

 $h = \frac{Total number of households counted}{Number of households to survey}$

- 5. Find the first HH to sample by randomly selecting a number between 1 and *h*. Random number selection can be done in the field by writing numbers on pieces of paper, folding them up, placing them in a container and mixing before drawing one out at random, and then selecting the HH that is on this row in the village list.
- 6. The second HH to sample should be the initial number + h
- 7. Sampling should then proceed in this manner with every h^{th} HH being sampled.

Example of selection of houses with a random walk (Worrell and Mathieu 2012):

Step 1

- 1. The protocol is to sample 4 HHs to in the village.
- 2. The central point of the village has been found (see diagram below).
- 3. The bottle has been spun and the direction of survey determined.
- 4. A total of 12 HHs have been found between the direction of the bottle and the village boundary (see step 1 in the diagram below).
- 5. Therefore h = 12 / 4 = 3.

Diagram illustrating a random walk with 12 HHs and 4 HHs to be interviewed

Step 2

- 6. The first HH to be surveyed is randomly selected between numbers 1 4 and is number 2. HH number 2 is identified, and is shown with a red star on the diagram above.
- 7. The second HH to sample is HH 2 + 3 = 5. This is shown with a yellow star on the diagram above.
- 8. Sampling then continues to HHs 8 (=5+3) and 11 giving 4 HHs sampled in total.

Obtaining household permission to survey

Once the HH has been selected for interviews, the survey team should approach the house in a friendly and respectful manner and follow the below steps:

- Ask to speak with the head of the HH or the most senior person present.
- Introduce yourself to the head of the HH
- Explain the purpose of your visit and obtain consent from the head of the HH. Ensure the introduction is factual and does not influence or bias the HH's responses

• See below for example introduction:

Hello, my name is <name>. I am here on behalf of the Ministry of Health of <country>, and we are here to conduct a household survey about an activity that has taken place in the village during the past months.

We would like to speak to some members of your households; and if you agree, the survey will only take a few minutes. Your answers will be treated anonymously.

The results will the Ministry of Health improve the programme.

It is your choice to take part, or not to take part, in this survey. If you do not wish to participate, it will not have any consequences for you.

Would you like to take part in our survey?

Answer: **Yes** or **No**.

- If the head of the HH provides consent, ask them to complete the household consent form (appendix C). If the person is not literate, read out the consent form in the local language, and obtain consent by thumb print.
- If the head of the HH **DOES NOT** provide consent for the survey; thank them for their time and continue to the next HH.

What to do if a household cannot be interviewed

If people in the selected home refuse to participate, try to encourage participation. If they still refuse, indicate this on the survey form, and count this HH as one of the HHs visited, indicate this on the survey form. **DO NOT replace the house with another HH**.

If no-one is at home in the selected HH, return later in the day. If, again, nobody is at home, indicate this on the survey form in the "Household questions" section, and count this HH as one of the HHs visited. **DO NOT** replace the HH with another one⁵.

If there are no eligible individuals for interview in the HH (e.g. no SAC live at the address, or all HH members moved in after the drug distribution), note this on the survey form, do not ask the questions, **but replace the HH with the next HH in the direction of travel with any eligible interviewee.**

Selecting individuals within a household

- If the head of the HH agrees to participate, proceed with the interview.
- Two adults and all school-aged children (SAC) within each HH will be randomly selected for interview.
- SAC is all children aged 5 -14 years
- Adults is all people aged 15 or over

The steps to take for interviewing SAC within a HH are:

- 1. Write the name of each SAC (i.e. all children aged 5 -14) in the HH on a separate piece of paper. Include all SAC living in the HH, even if they are not in the HH at the time.
- 2. Begin interviewing the children who are available for interview

⁵ If this happens for many households (e.g. frequently >2 households/village) in several villages, the supervisors should discuss with the study co-ordinator to consider increasing the number of households to randomly select per village.

3. If a selected individual cannot be interviewed, record who they are and please see below.

The steps to take for interviewing adults within a HH are:

- Write the name of each adult (i.e. all individuals 15 or over) in the HH on a separate piece of paper.
 Include all adults living in the HH, even if they are not in the HH at the time.
- 2. Fold up the pieces of paper and put into a container
- 3. Pick out two pieces of paper
- 4. Interview the adults whose names are on the paper
- 5. If a selected individual cannot be interviewed, please see below

What to do if an individual cannot be interviewed

- If an individual (SAC or adult) cannot be interviewed then return later to try to interview them.
- If an individual is away from the house (e.g. at school), go to try to find them if permission from the head of the HH has been obtained.
- If they still cannot be interviewed then DO NOT replace them with another individual. Record them on the survey form as not being interviewed and the reason why.

Interviewing selected individuals

- Interview the randomly selected individuals using the phones or paper forms
- Interviews should be conducted with each person privately; parents can accompany children.
- Avoid leading questions or providing the HH with information which later you will be asking them to provide to you either as an answer, or to check their responses. Use visual cues as much as possible (dose poles, drugs etc)
- **DO NOT** read the multiple-choice options to the interviewee or suggest an answer
- Wait for the interviewee to provide an answer and then choose the most appropriate option on the phone or from the codes provided with the paper forms
- If using paper forms, be very careful when answering questions with multiple parts that no contradictory answers are given e.g. person says that they did take drugs but also give a reason why they didn't take drugs

Note: The survey can be conducted by either one (1) or both interviewers at a time. If the interviewers feel confident that they can conduct the interview alone then the other interviewer and field supervisor can proceed to the next HH according to the sampling protocol.

Finishing the survey

- After everyone selected has been interviewed and all the responses recorded on the data collection form thank everyone for their assistance and leave the HH.
- Move on to the next selected HH and repeat.

